14.4 Handling of missing data

Missing data of safety or pharmacokinetics variables will not be replaced. Details on the handling of missing data will be specified in the SAP.

14.5 Interim analysis

No formal interim analysis will be performed.

14.6 Sample size justification

Thirty-two (32) subjects will be included in this study, stratified into two groups of 16 subjects each. One of the groups will receive PDT applying 3 tubes of BF-200 ALA in the face/scalp, the other group will receive PDT applying 3 tubes of BF-200 ALA on the neck/trunk/extremities.

A previous PK Phase I study under maximal use conditions in AK subjects with 1 tube of BF-200 ALA (ALA-AK-CT006) had revealed homogeneous baseline-adjusted levels of ALA and PpIX in 12 subjects, with a CV of 53-73% in the key pharmacokinetic parameters after drug application. As statistical evaluation of PK and safety is intended to be performed as descriptive statistics only, no calculation of predictive power is required.

Based on the results of a previous PK study (ALA-AK-CT006), a group size of 12 subjects is considered to be sufficient for proper pharmacokinetic evaluation and in agreement with the findings from the pilot study. In order to compensate for potential drop-outs of subjects as well as potentially higher variability of data due to combined investigation of two treatment

areas, stratum size was adapted from 12 to 16 subjects. A drop-out rate of 25% (4 of 16 patients) was assumed taking into account the complex nature of the study procedures comprising PDT treatment with three tubes and up to two illuminations, and frequent blood sampling on one single day. For this reason, the sample size of 32 subjects is considered to be adequate for pharmacokinetic evaluation in this PK study.

15 ETHICAL AND LEGAL ASPECTS

15.1 Good clinical practice

This study is to be conducted according to globally accepted standards of GCP (as defined in the ICH E6 (R2) Guideline for GCP), in agreement with the Declaration of Helsinki in its current version and in keeping with local regulations.

15.2 Delegation of investigator duties

The investigator should ensure that all persons contributing to the trial are adequately qualified, informed about the protocol, any amendments to the protocol, the study treatments, and their trial-related duties and functions.

The investigator should immediately report any changes in study personnel to the sponsor. Any regulatory requirement regarding a change in site personnel has to be met. Besides that, the investigator should maintain a list of subinvestigators and other appropriately qualified persons to whom they have delegated significant trial-related duties.

If required by local regulations, the investigator should designate a deputy investigator with appropriate qualifications being able to fully replace the investigator in cases of absence.

15.3 Subject information and informed consent

Every trial participant will receive a complete and comprehensive explanation of the significance, nature, extent, and possible risks of the trial. To this end, a detailed, written subject information sheet will be made available. In addition, an investigator/subinvestigator will carry out an oral information session during which the subjects will be given ample time and opportunity to clarify remaining questions.

Afterwards, the subject or their legal representative and the investigator/subinvestigator will sign the informed consent form (ICF). To grant direct access to the subject's original medical records for verification of clinical trial procedures and/or data, without violating the confidentiality of the subject, the subject/legal representative will also sign an agreement. Depending on the local legal requirements this agreement can be part of the ICF or a separate form, such as the HIPAA form. The original signed ICF and, if applicable, HIPAA forms will be archived in the ISF. The subject will receive a copy of these documents. The investigator will acknowledge instruction of every subject in accordance with the clinical study protocol (CSP) and the existence of a signed consent and HIPAA form.

Before valid consent has been obtained the subject will not undergo any study related procedures. The investigator should inform the subject's primary physician about the subject's participation in the trial if the subject agrees to this.

During the course of the trial, ICF may need to be updated and thus, requires re-consenting of subjects. The investigator /subinvestigator will inform every active trial participant in a timely manner and obtain updated ICF in line with above mentioned obligations.

15.4 Confidentiality

To ensure confidentiality the subject's data will be collected for the clinical data base and analysis in a strictly pseudonymous form, i.e. using a subject number instead of the subject's

name. The subject number will also be used for SAE reporting purposes. On supporting documents of an SAE report, such as hospital reports or laboratory reports, the subject's name and if required by regulations the physician's name has to be obliterated.

The investigator will maintain a personal subject identification list (subject numbers with the corresponding subject names) to enable records to be identified.

Subject identity and personal data will be safeguarded according to national requirements on data protection.

The sponsor adheres to data protection regulations.

15.5 Protocol deviations

Protocol deviation have to be documented and explained by the investigator and/or the sponsor. Major protocol deviations have to be escalated to the sponsor. If there is a legal requirement, the investigator needs to report major protocol deviations to the responsible ethics committee (EC)/IRB.

The sponsor is obliged to report serious breaches (severe violations of GCP regulations as well as all events that affect to a significant degree, the safety or physical or mental health of the subjects of the trial or the scientific value of the trial) to the IRB(s) and the applicable authorities.

15.6 Protocol amendments

The investigators cannot alter the protocol without the sponsor's approval. If the sponsor amends the protocol all principal investigators need to agree to adhere to the amended protocol.

In case of protocol changes that might affect the subjects' safety and well-being or the validity and integrity of the study data, the amendment is deemed substantial. Minor changes to the protocol, such as administrative changes, correction of typos and inconsistencies etc. stipulate a non-substantial amendment.

15.7 Approval of the clinical study protocol and amendments

Prior to the start of the study, the CSP, subject information leaflet and ICF, and any other appropriate documents will be submitted to the IRB(s) in charge. If applicable, the documents will also be submitted to the authorities, in accordance with local legal requirements.

All ethical and legal requirements must be met before the sites can start enrolling subjects.

A protocol amendment has to be submitted to the IEC/IRB and, if required, to the regulatory authority(ies). In case of a non-substantial amendment these bodies only will be notified but they need to approve any substantial amendment to the protocol before it can be implemented. Amendments must be evaluated to determine whether the subject information leaflet and informed consent form should also be revised.

The investigator must keep a record of all communication with the IRB(s) and, if applicable, between a Coordinating Investigator and the IRB(s). This also applies to any communication between the investigator (or Coordinating Investigator, if applicable) and the authorities.

15.8 Ongoing information for ethics committee/institutional review board

Periodic reports (e.g. annually) will be generated and submitted regarding to the requirements of the respective IRB or any applicable law(s) for IRB continuing review.

15.9 Closure of the study

Upon study completion or premature termination, each investigational site will be closed.

Completion or premature termination of the study will be reported to the regulatory agency and to the IRB if required by local regulation or by the IRB(s).

Furthermore, the sponsor has the right to close a study site at any time. As far as possible, premature closure should occur after mutual consultation.

Study materials must be returned, disposed of, or retained as directed by the sponsor.

15.10 Record retention

At the close-out visit the monitor will inform the sites about the required archiving period. The investigator must obtain approval in writing from the sponsor prior to destruction of any records and must document any change of ownership.

Within the United States of America the investigator has a legal obligation to retain records required to be maintained under 21 CFR §312.62 for a period of 2 years, following the date a marketing application is approved for the drug and the indication for which it is being approved. In case no application is to be filed or if the application is not approved for such indication, records will be kept for two years after the investigation is discontinued and FDA is notified.

This regulation applies to:

- Adequate and accurate case histories that record all observations and other data pertinent to the investigation on each individual administered IMP and PDT such as:
 - Case report forms and supporting data.
 - Signed and dated consent forms.
 - Medical records including e.g. progress notes of the physician and nurse.
 - The case history of each subject shall document that informed consent was obtained prior to participation in the study.
- Records documenting disposition of the IMP and IMD (including dates, quantity, use and return to the sponsor) if the investigation is terminated, suspended, discontinued or completed.

15.11 Liability and insurance

Liability and insurance provisions for subjects will be arranged according to legal requirements. If required by legal requirements, the subjects will receive a copy of the general conditions of insurance. Liability and insurance provisions for investigators participating in this study will be defined in a separate agreement, if applicable.

15.12 Financial disclosure

Prior to the start of the study, the investigator will disclose to the sponsor any proprietary or financial interests he or she might hold in the IMP, the IMD or the sponsor company as outlined in the financial disclosure forms (e.g. Form FDA 3454 or FDA 3455). By signing the financial disclosure form the investigator is also obliged to inform the sponsor about any changes up to one year after study completion/termination.

Where required by regulation, the sponsor will also submit the financial arrangements for the study to the regulatory authorities and if applicable to the IRB(s). Similar information will be provided by each subinvestigator to whom the investigator delegates significant study-related responsibilities.

16 QUALITY CONTROL, QUALITY ASSURANCE, AND INSPECTIONS

Quality control mechanisms are implemented on a functional level and quality assurance audits will be done according to GCP (ICH Topic E6 (R2) GCP guideline) and the applicable regulatory requirements. Direct access to the on-site study documentation and medical records must be ensured.

16.1 Study monitoring and source data verification

Monitoring is the act of overseeing the progress of a clinical trial, and of ensuring that it is conducted, recorded, and reported in accordance with the protocol, SOPs, GCP, and the applicable regulatory requirement(s). The frequency of monitoring and co-monitoring visits, and the degree of source data verification are defined in the monitoring plan. Monitoring will be done by onsite visits. In addition to the monitoring visits, frequent communications (letter, telephone, and fax) by the clinical monitor will ensure that the investigation is conducted according to protocol design and regulatory requirements.

The results of monitoring visits will be documented in monitoring reports. Issues arising will be escalated and dealt with in a timely manner. The escalation process is defined in the respective SOPs of the contract research organization (CRO) or sponsor.

Study closeout will be performed by the clinical monitor upon closure of the study.

16.2 Site audits

Audits can be conducted at any time during or after the trial to assure the validity and integrity of the study data, the protection of the right, safety and well-being of the subjects and the adherence to the protocol, to ICH-GCP, ISO 14155 (if applicable) and to the applicable legal requirements. On-site audits will be conducted by an independent auditor from the respective quality assurance unit of the CRO or the sponsor or by a contracted auditor. Direct access to these documents must be guaranteed by the investigator, who must provide support at all times for these activities.

16.3 Site Inspections

Domestic and foreign regulatory authority(ies) may conduct an official review of documents, facilities, records, and any other resources that are deemed by the authority(ies) to be related to the clinical trial and that may be located at the site of the trial. For this, the investigator/institution has to give access to all source documents, eCRFs, and other study documentation for an inspection. The investigator should inform the sponsor as soon as possible about any announced inspection. Site personnel should fully comply with inspection procedures.

17 DOCUMENTATION AND USE OF STUDY FINDINGS

17.1 Documentation of study findings

This study will be performed using an eCRF. The investigator and study site staff will receive system documentation, training, and support for the use of the eCRF.

All protocol-required information collected during the study must be entered by the investigator, or a designated representative, in the eCRF as soon as possible, preferably on the same day that a study subject is seen for an examination, treatment, or any other study procedure. Any outstanding entries must be completed immediately after the final examination. An explanation should be given for all missing data. All data entry, modification or deletion will be recorded automatically in an electronic audit trail, indicating the individual subject, original value, the new value, the reason for change, who made the change, and when the change was made. All data changes will be clearly indicated with a means to locate prior values. The system will be secured to prevent unauthorized access to the data or the system. This will include the requirement for a user identification and password to enter or change data. The investigator will maintain a list of individuals who are authorized to enter or correct data and their system identification.

All electronic data entered by the site (including an electronic audit trail) as well as computer hardware and software (for accessing the data) will be maintained or made available at the site in compliance with applicable record retention regulations. The computerized system is able to generate accurate and complete copies of records in both human-readable and electronic form for inspection, review, and copying by regulatory authorities, the IRB(s), and auditors authorized by the sponsor. Site documentation will identify the software and hardware systems used to create, modify, maintain, archive, retrieve, or transmit data.

A source data location list will be prepared and updated during the study. It will specify which types of source data are available and where they are stored (e. g. electronic or paper subject files etc.), and which data may be entered directly into the eCRF. This list will be filed in both the TMF and the investigator study file and updated as necessary. The sites can establish appropriate work sheets or record the source data directly in subjects' notes. Source data entries have to be signed and dated by the respective investigator or delegated person in compliance with the delegation log in which responsibilities and duties of the study performance are laid down. In addition, all changes and additional entries have to be made visible and signed and dated by the respective study team member.

The investigator, or designated subinvestigator, following review of the data in the eCRF, will confirm the validity of each subject's data by electronic signature. The sponsor will retain the original eCRF data and audit trail. A copy of all eCRFs completed by the site will be provided to the concerned investigator.

17.2 Use of study findings

All information concerning the product as well as any matter concerning the operation of the sponsor, such as clinical indications for the drug or medical device, the drug formula, methods of manufacture and other scientific data relating to it, that have been provided by the sponsor and are unpublished, are confidential and must remain the sole property of the sponsor. The

investigator will agree to use the information only for the purposes of carrying out this study and for no other purpose unless prior written permission from the sponsor is obtained.

The sponsor has full ownership of the eCRFs completed as part of the study.

By signing the CSP, the investigator agrees that the results of the study may be used for the purposes of national and international registration, publication, and information for medical and pharmaceutical professionals. The authorities will be notified of the investigator's name, address, qualifications, and extent of involvement.

The sponsor will ensure that a final report on the study is prepared.

As required by local regulation or by the IRB(s), a summary of the clinical study will be submitted by the sponsor to the regulatory authorities and by the sponsor or investigator to the IRB(s).

The Coordinating Investigator of a multi-center trial or the Investigator in a single-center trial will be required to sign a statement in the clinical study report in which he or she confirms that, to the best of his or her knowledge, it accurately describes the conduct and results of the study.

All materials, documents, and information supplied by the sponsor to the investigator, and all materials, documents, and information prepared or developed in the course of the study to be performed under this protocol, shall be the sole and exclusive property of the sponsor.

Scientific publication of the study results may be planned mutually between the sponsor and the Investigator. Details of the publication policy will be specified in the investigator contracts.

19 APPENDICES

Appendix A: Fitzpatrick's Skin Type Test according to Fitzpatrick (1988)

Appendix B: NRS-11 for pain during PDT

APPENDIX A

Fitzpatrick's Skin Type Test

Fitzpatrick's Skin Type according to Fitzpatrick, 1988 (38)

One of the important parameters for the success of your treatment is the correct typing of your skin.

Skin type is often categorized according to the Fitzpatrick skin type scale, which ranges from very fair (skin type I) to very dark (skin type VI). The 2 main factors that influence skin type and the treatment program devised by your doctor are:

- Genetic disposition -Skin types I to III should add one level when you have blood relatives with darker skin type IV or higher.
- Reaction to sun exposure and tanning habits.

Skin type is determined genetically and is one of the many aspects of your overall appearance, which also includes color of eyes, hair, etc. The way your skin reacts to sun exposure is another important factor in correctly assessing your skin type. Recent tanning (sun bathing, artificial tanning or tanning creams) have a major impact on the evaluation of your skin color.

So, please help us determine your skin type to assist us in your treatment.

Genetic disposition					
Score	0	1	2	3	4
What is the color of your eyes?	Light blue, Gray, Green	Blue, Gray or Green	Blue	Dark Brown	Brownish Black
What is the natural color of your hair?	Sandy Red	Blond	Chestnut/ Dark Blond	Dark Brown	Black
What is the color of your skin (non exposed areas)?	Reddish	Very Pale	Pale with Beige tint	Light Brown	Dark Brown
Do you have freckles on unexposed areas?	Many	Several	Few	Incidental	none

Total score for genetic disposition: _____

Fitzpatrick's Skin Type Test

(cont.)

Reaction to sun exposure					
Score	0	1	2	3	4
What happens when you stay in the sun too long?	Painful redness, blistering, peeling	Blistering followed by peeling	Burns sometimes followed by peeling	Rare burns	Never had burns
To what degree do you turn brown?	Hardly or not at all	Light color tan	Reasonable tan	Tan very easy	Turn dark brown quickly
Do you turn brown within several hours after sun exposure?	Never	Seldom	Sometimes	Often	Always
How does your face react to the sun?	Very sensitive	Sensitive	Normal	Very resistant	Never had a problem

Total score for reaction to sun exposure: _____

Fitzpatrick skin type will be assessed according to skin type score as follows:

[figure not shown]
Skin Type Score	Fitzpatrick Skin Type
0 – 7	I
8 – 16	II
17 – 24	III
25 – 30	IV
>30	V – VI

APPENDIX B

Numeric rating pain scale for pain during photodynamic therapy

Pain sensation during photodynamic therapy (PDT) will be assessed using the 11-point numeric rating pain scale, shown below:

Please rate your pain intensity by circling the number that best describes your maximum pain during PDT.

To be transferred into the 4-point scale if applicable 0= none, 1-3 = mild, 4-7 = moderate, 8-10 = severe.

4.7 Miscellaneous	12
5 CHANGES FROM PROTOCOL	14
6 SIGNATURES	15

List of Abbreviations

In the following abbreviations are listed as used within this statistical analysis plan or which might occur within the tables, listings and graphs outputs:

ADaM	Analysis Data Model
AE	Adverse event
AK	Actinic keratosis
ALA	5-aminolevulinic acid
ATC	Anatomical therapeutic chemical classification
AUC _{0-∞}	Area under the curve (parameter for PK analysis)
BMI	Body mass index
C _{max}	Maximal plasma concentration (parameter for PK analysis)
CDISC	Clinical Data Interchange Standards Consortium
CRF	Case report form
CS	Clinically significant
CV	Coefficient of variation
eCRF	Electronic case report form
ENR	Enrolled set
EoS	End of study
FSFV	First subject first visit
GmbH	Gesellschaft mit beschränkter Haftung, Ltd, limited liability company
ICH	International council of harmonization
IMP	Investigated medical device
MedDRA	Medical dictionary for regulatory activities
N	Number of subjects
NRS-11	Numeric Rating Scale (11-point pain rating scale)
PDT	Photodynamic therapy
PK	Pharmacokinetic(s)
PP	Per-protocol
PpIX	Protoporphyrin IX
PT	Preferred term
SAE	Serious adverse event
SAF	Safety analysis set
SAP	Statistical analysis plan
SD	Standard deviation
SDTM	Study Data Tabulation Model
SOC	System organ class
T _{1/2}	Terminal half-life after last administration (parameter for PK analysis)
TEAE	Treatment emergent adverse event
TLG	Tables, listings, graphs
T _{max}	Time of maximum concentration (parameter for PK analysis)
Treatment area	Body area in which the treatment field is located
Treatment field	Area within the illumination area to which the medicinal product was applied
TS	Treated set
WHO-DD	World Health Organisation-Drug dictionary
λ _z	Terminal rate constant after last administration (parameter for PK analysis)

1 General

This Statistical Analysis Plan (SAP) was defined by the Sponsor and the responsible Statistician. It is based upon the Study Protocol (version 2.0 of 17Jan2020) and contains detailed description of the statistical methods described therein.

The SAP describes prospectively the analyses to be performed on study data after database lock. It was finalized prior to enrolment of first subject.

The assessment and analysis of pharmacokinetics is covered in a separate SAP and is not part of this SAP.

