14. Impaired renal function (Glomerular filtration rate below 50 mL/min/1.73m² estimated by Modification of Diet in Renal Disease equation (MDRD)).
15. Positive test for HIV antibodies, Hepatitis B-virus surface antigen (HBsAg) or positive Anti-hepatitis C-virus antibody (Anti-HCV) test.

16. Significant blood donation or blood loss (≥ 500 mL) within three months prior to Visit 2.
17. Breast-feeding women.
18. Subject unlikely to comply with the protocol, e.g. inability to return for visits, unlikely to complete the study, or inappropriate in the opinion of the investigator.
19. Prior participation in the study (participation is defined as having been screened).
20. A member of study site staff or sponsor staff directly involved in the conduct of the protocol or a close relative thereof.
21. Simultaneous participation in a further clinical study.

Reassessment of subjects is allowed once if sunburn, wounds, irritations, bleeding or skin infections detected at Visit 1 are expected to resolve within the screening period. Reassessment can be done on the day of the actual treatment.

Dosing day exclusion criteria:

1. Febrile or infectious illness within 7 days prior to Visit 2.
2. Subjects with sunburn, wounds, irritations, bleeding or other confounding skin conditions within illumination areas at Visit 2.
3. Use of topical NSAIDs inside and outside the treatment field(s) or systemic intake of NSAIDs within 7 days prior to Visit 2.

In case a subject meets one of the dosing day exclusion criteria, Visit 2 can be rescheduled once within 14 days. Meeting any of the dosing day exclusion criteria on the rescheduled visit will lead to discontinuation of the trial.

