3.1 Enrolled set (ENR)

All subjects enrolled in this study i.e. that provided informed consent to participate in the study.

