3.2 Enrolled set 2 (ENR2)

All subjects enrolled in this study i.e. that provided informed consent to participate in the study will be included once. Due to COVID-19 implications 2 eligible subjects could not be treated within the visit window. Thus, these subjects were documented as drop-outs and re-screened later. Within enrolled set 2, these subjects will be included with their 2nd screening ID only.

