--------------------------------	----------------------------

All tables, listings, and graphs will be generated in A4 paper format.

[figure not shown]
The statistical evaluation will be performed using SAS version 9.4 or higher.

5 Changes from Protocol

In the following any changes on statistical aspects as described in the protocol are given:

- The protocol version 2.0 of 17Jan2020 states in section 14.3, that confidence intervals will be presented for maximal pain score. As all planned analyses are of exploratory nature and without any formal statistical hypotheses, no confidence intervals will be conducted.
- In addition to the analysis sets specified in protocol version 2.0 of 17Jan2020, the analysis set 'Enrolled 2' is defined.

6 Signatures

Statistician:

Date (ddmmmyyyy)
Signature

Sponsor:
 Biofrontera Bioscience GmbH Head Clinical Trial Project Management [name] [name] Germany
Date (ddmmmyyyy)
Signature

Sponsor:
 Biofrontera Bioscience GmbH Project Manager Clinical Trials [name] [name] Germany
Date (ddmmmyyyy)
Signature

TITEL PAGE SAP PK, V2.0 DATED 21-SEP-2020

Study ALA-AK-CT015,

NCT04319159

An open-label Phase I study to evaluate the pharmacokinetics of 5-aminolevulinic acid and protoporphyrin IX in human plasma under maximal use conditions after topical application of 3 tubes of BF-200 ALA 10% gel for photodynamic therapy (PDT) in subjects suffering from actinic keratosis

Statistical Analysis Plan for Pharmacokinetics

Study title: An open-label Phase I study to evaluate the pharmacokinetics of 5-aminolevulinic acid and protoporphyrin IX in human plasma under maximal use conditions after topical application of 3 tubes of BF-200 ALA 10% gel for photodynamic therapy (PDT) in subjects suffering from actinic keratosis

Protocol Number: ALA-AK-CT015

Version: Final 2.0
Date: 21-SEP-2020

PREPARED BY:

Senior Biostatistician

Date

REVIEWED BY:

Team Lead Programming

Date

APPROVED:

Director of Exploratory Development
Biofrontera Bioscience GmbH

Date

INDEX

1. INTRODUCTION	3
2. RESPONSIBILITIES	3
3. STUDY OBJECTIVES AND ENDPOINTS.....	3
4. DESIGN OF THE STUDY	4
5. SAMPLE SIZE AND POWER ESTIMATION.....	4
6. ANALYSIS SETS	4
7. PRESENTATION OF DATA	5
8. SOFTWARE	5
9. DEMOGRAPHIC DATA AND BASELINE CHARACTERISTICS.....	5
10. PHARMACOKINETIC PARAMETERS.....	5
10.1. Tabulation of Individual Data	7
11. STATISTICAL METHODOLOGY FOR PHARMACOKINETIC ENDPOINTS	7

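### Do the safety SAP's wrong finalisation statement and its treatment of two re-screened subjects put any safety result at risk?

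*SAP*

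**What the plan says.** Section 1 of the safety SAP states: "It was finalized prior to enrolment of first subject". The same section leaves pharmacokinetics to a separate SAP. Section 3.1 defines the enrolled set (ENR) as "All subjects enrolled in this study i.e. that provided informed consent to participate in the study".

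Section 3.2 adds enrolled set 2 (ENR2) and gives the reason: "Due to COVID-19 implications 2 eligible subjects could not be treated within the visit window". It continues: "Thus, these subjects were documented as drop-outs and re-screened later". The rule is then: "Within enrolled set 2, these subjects will be included with their 2nd screening ID only". Section 5 opens with "In the following any changes on statistical aspects as described in the protocol are given" and names two changes. One drops the confidence intervals for the pain score. The other reads: "In addition to the analysis sets specified in protocol version 2.0 of 17Jan2020, the analysis set 'Enrolled 2' is defined".

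On AEs:

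- Protocol 11.2 starts collection at consent. Before Visit 2 it covers events suspected to be caused by study procedures.
- Protocol 14.3 promises a listing of all reported AEs for all enrolled subjects.
- SAP 3.6 puts safety analyses on the SAF, and SAP 4.7 makes the SAF the default for listings. Both allow exceptions stated elsewhere, and SAP 3.6 names the appendix.
- SAP 4.7 lists the outputs that also cover enrolled but untreated subjects: analysis sets, eligibility, visits, demographics and discontinuation.
- SAP 4.4.2 provides a separate listing of AEs with onset more than one hour before gel application.

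**The concern.** A plan that was final before the first consent could not describe, in the past tense, what later happened to two consented subjects. A reader who relies on the section 1 sentence would think that every analysis set was fixed before any data existed.

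The second worry is a lost event. Suppose a subject has a procedure-related AE at the first screening, is recorded as a drop-out, and is later treated under a new ID. The first record has no treatment procedure, so it is outside the SAF and the treatment-emergent tables. It has no application time, so it does not fit the rule for the separate pre-treatment listing. SAP 4.5 would call the event treatment-emergent because the application date is missing, but those tables use the SAF. Read literally, the event appears nowhere, and section 5 does not declare this as a departure from protocol 14.3.

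Two side issues add to the unease. Exclusion criterion 19 bars anyone already screened. Protocol 14 treats withdrawal before treatment as screening failure, with little data entered and no cleaning, whereas SAP 3.2 speaks of drop-outs.

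**Working it through.** **Timing.** SAP 1 and SAP 3.2 cannot both hold for the same text. What depends on the date is limited:

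- ENR2 is used, together with ENR, only for the disposition of subjects to analysis sets (SAP 3.6).
- All analyses are exploratory, without hypotheses (SAP 4), in an open-label study in which everyone gets the same treatment.
- The primary and tertiary endpoints and the secondary pharmacokinetic parameters belong to the separate SAP.
- The allocation of subjects to sets is decided at a data review before database lock (SAP 4.6).

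Adding ENR2 after enrolment began therefore changes a count of screening records and nothing else.

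**How many records.** The planned size reproduces: 12 / (1 - 0.25) = 16 per stratum, and 2 × 16 = 32. ENR and ENR2 differ by 2 records. The documents do not say whether the two subjects were later treated. If 32 are treated and each screening ID is counted as a subject:

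| Re-screened subjects treated | ENR at least | Records outside AE output, at least |
|---|---|---|
| both | 32 + 2 = 34 | 2/34 = 5.9% |
| neither | 32 + 2 × 2 = 36 | 4/36 = 11.1% |

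These are shares of records, not of AEs. Other enrolled but untreated subjects would add to them; their number is not given.

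**How many events.** Screening takes 3 + 2.7 + 5 + 7.5 = 18.2 mL of blood for safety tests (protocol 10.2.7). With 3 + 7.5 = 10.5 mL at Visit 3, this reproduces the protocol's total of 28.7 mL. The pharmacokinetic sample adds about 10 mL, so one screening takes about 28.2 mL. A procedure-related AE is possible, but the documents give no rate. Assuming 2-10% per record, the expected number is 0.02 × 2 = 0.04 to 0.10 × 4 = 0.4. The likeliest number is none.

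**Is the gap in the AE listing certain?** Three readings weaken it:

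1. Appendix A holds the detailed listings and may assign another set. It was not supplied.
2. The SAF is defined by subjects, and SAP 3.2 speaks of subjects who have a second screening ID. If the two IDs are linked by person and the person was treated, an application time exists. A first-screening AE then falls into the separate listing of SAP 4.4.2, and with both subjects treated none of these records is left out.
3. The protocol itself points both ways. Section 14.2 makes the SAF the set for all safety analyses. Section 14.3 speaks of listing the variables of treated subjects and refers safety data to the SAF, before it promises the listing for all enrolled.

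**Side issues.** Violations of eligibility criteria already go to the data review, and the deviations found there are listed (SAP 4.6). AE entry does not depend on the label. Table 1 of the protocol schedules AEs and eCRF entry at Visit 1, section 11.3 requires all AEs to be documented, and section 12.1 sets only a minimum for untreated subjects. Nor is drop-out clearly the wrong word: protocol 7.5 ties screening failure to eligibility that cannot be confirmed, and these two subjects were eligible.

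**The case for a change.** The strongest case for a change is that the trace through the SAP text is sound. Section 4.7 deals with enrolled but untreated subjects explicitly and leaves AEs out. The protocol sentence on the AE listing is more specific than its general statements about treated subjects and the SAF. No rule in the SAP links the two screening IDs, and the contrast between ENR and ENR2 shows that enrolment is counted by ID. Section 5 sets out to give any change and does not give this one. The remedy would cost one listing on a wider set and a corrected date.

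Much of this stands. The section 1 sentence is wrong for this version, although an earlier version of the SAP may have been final in time, and a version history may sit in the front matter that was removed. The protocol and the SAP do not match on the listing. What does not follow is any consequence for the results. The secondary safety objective is the safety and tolerability of the photodynamic treatment. An AE under an ID that never received gel or light carries no information on that, and a serious one must be reported to the sponsor within 24 hours whatever the listing shows (protocol 11.3.1.1). Changing the default set would move, at most, a rare pre-treatment event from the database into a listing.

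**Conclusion.** No change to the plan follows. The finalisation statement is a clerical slip, most simply explained as a sentence carried over when ENR2 was added, and ENR2 itself is openly declared. The AE listing is a small gap that an analyst with protocol 14.3 at hand can fill sensibly when the listings are produced. The criterion 19 point is already covered by the data review, and nothing is gained by settling the drop-out label.

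At stake are an expected 0.04 to 0.4 pre-treatment AEs in 2 to 4 unexposed records, or fewer if the two IDs are linked by person. This rests on 32 treated subjects and on an assumed AE chance of 2-10% per record, for which the documents give no source. It leaves out other untreated enrolled subjects, who are just as unexposed. Whether either re-screened subject was later treated or had an AE is unknown, and the content of Appendix A is unknown. None of these unknowns can alter a pharmacokinetic result, a treatment-emergent AE table or a conclusion on the safety of the treatment.
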